# 5.2 Secondary Objectives:

- i. To compare the real life effectiveness of adalimumab to topical and traditional systemic agents in the prevention of development of articular and extra-articular manifestations in patients with moderate to severe Plaque PS.
- ii. To describe the profile and regional variation in terms of demographics, disease parameters, flare up trigger, comorbidities and concomitant medication use of Canadian patients with moderate to severe Plaque PS.
- iii. To describe the current practices and regional variation among Canadian dermatologists with respect to the screening and detection of articular manifestations indicating onset of PsA in patients with moderate to severe Plaque PS.

- iv. To describe the incidence of and risk factors for the development of articular and extra-articular manifestations in Canadian patients with moderate to severe Plaque PS.
- v. To describe the current population based burden of illness incorporating Health Care Utilization, Health Care Costs, Quality of Life, Psychological impact Work Productivity of moderate to severe Plaque PS in Canada.
- vi. To assess the impact of topical agents, traditional systemic agents and adalimumab on the Plaque PS related burden of illness incorporating Health Care Utilization, Health Care Costs, Quality of Life, Psychological impactWork Productivity in Canada.
- vii. To provide an ongoing assessment of the safety and tolerability of adalimumab, systemic and topical agents used in the management of moderate to severe Plaque PS in Canada.

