- ix. Change in Work Limitation Questionnaire at 6, 12 and 24 months. The WLQ is a self-administered questionnaire comprised of 25 questions. It assesses the degree to which the patient's work is affected due to health problems or health-related productivity loss. The 25 questions are further divided into four scales: time management, physical demands, mental-interpersonal demands and output demands. The scoring for the WLQ ranges from 0 (none of the time) to 100 (all of the time) and represent the portion of time in the prior two weeks that those answering the questionnaire were limited in their abilities while at work. Furthermore, an algorithm is present that can convert scores obtained using the WLQ into an estimate of productivity loss. Considering the important effect of psoriasis on the patient's ability to deal with the emotional and physical demands of employment, the assessment of the impact of disease and treatment on work related productivity loss is highly relevant.
- x. Health Care Utilization Questionnaire through the 24 months of treatment. This will be a descriptive self administered series of questions aimed at measuring the patient's health care utilization and economic impact of the disease. More specifically the questionnaire will ascertain the frequency of physician visits, utilization of other health care professionals, visits to clinics, emergency rooms and hospitalizations that are related to psoriasis. In addition, use of prescription and non–prescription medications for the management of psoriasis will be determined. Out of packet expenses for medications and health care will be assessed. The patient's occupation and household income range will be used as a proxy to socioeconomic status.
- xi. Compliance with treatment will be assessed through the 24 months of treatment

by self report of missed topical applications, medication doses or adalimumab injections.

- xii. Change in medical history and concomitant medication use through the 24 months of treatment will be recorded assessed by the treating physician as per routine care.
- xiii. Use and frequency change of phototherapy for psoriasis through the 24 months of treatment will be ascertained by a targeted question in the patient assessment.

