#### Physical Examination and Medical History:

During the baseline assessment the results of a complete physical examination and medical history will be recorded in the study Case Report Form. For subsequent follow up assessments, only clinically important changes in the Medical History and Physical Examination will be recorded.

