#### 7.0 Adverse Events

The primary aim of the current PMOS is to assess real life effectiveness. Given that the primary objective is not to assess any safety parameters only spontaneously reported Serious Adverse Events (SAEs), unusual failure in efficacy and Pregnancies must be reported.

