## 7.2 Severity

The physician will use the following definitions to rate the severity for any adverse event being collected as an endpoint/data point in the study and for all serious adverse events.

Mild The adverse event is transient and easily tolerated by the subject.

Moderate The adverse event causes the subject discomfort and interrupts the subject's usual activities.

Severe The adverse event causes considerable interference with the subject's usual activities and may be incapacitating or life-threatening.

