In order to better assess the impact of the treatment received and changes in the regimen the treatment will be handled as a time – dependent covariate in these analyses.

With respect to achieving therapeutic response end points and incidence of articular and extra-articular manifestations between group differences will be assessed with multivariate logistic regression while Cox proportional hazard models will be used to assess between group differences with respect to the time of achieving therapeutic response and first occurrence of articular and extra-articular manifestations.

Descriptive statistics will be used to assess the between group and regional differences with respect to patient characteristics and disease parameters. Descriptive statistics will also be used to assess the practice patterns of Canadian dermatologists in the management of patients with moderate to severe PLAQUE PS. The study cohorts will be divided into Canadian regions as Quebec, Ontario, Maritimes and Western Canada.

Underdiagnosis of articular and extra articular manifestations will be assessed by the prevalence of existing articular manifestations and a survey of participating physicians with respect to their estimates of the prevalence of articular and extra- articular manifestations in the patients.

Safety will be assessed by the incidence of treatment emergent adverse events with adjusted relative risks used to compare the three treatment groups.

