### 2.10.2 Safety Measures

Safety and tolerability will be assessed with the incidence of treatment-emergent adverse events. Incidence of treatment emergent serious adverse events will be recorded by the treating physician through the 24 months of treatment. Severity of the adverse event and causal relation to the treatment will be assessed by the treating physician. All adverse events will be coded as per the MedDRA dictionary of terms.

i. All serious adverse events will be recorded and reported as per regional regulatory guidelines and requirements.

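### The planned safety measure is treatment-emergent adverse events of any seriousness, but the visible collection rules require only spontaneously reported serious events, and the SAP lists no safety method or table

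*Protocol*

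**What the plan says.** The analysis text is broad. Protocol 10.2 says "Safety will be assessed by the incidence of treatment emergent adverse events with adjusted relative risks used to compare the three treatment groups". SAP 2.10.2 agrees on the measure, "Safety and tolerability will be assessed with the incidence of treatment-emergent adverse events", but does not mention relative risks. Both serve a stated secondary objective (Protocol 5.2 vii, repeated as SAP objective 5): "To provide an ongoing assessment of the safety and tolerability of adalimumab, systemic and topical agents used in the management".

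The collection text is narrower. Protocol 7.0 sets the reporting duty with the words "the primary objective is not to assess any safety parameters only spontaneously reported Serious Adverse Events", and adds unusual failure in efficacy and pregnancies as the only other reportable items. The SAP sentence that follows the measure reads: "Incidence of treatment emergent serious adverse events will be recorded by the treating physician through the 24 months of treatment". The same SAP section then extends MedDRA coding to every adverse event. Protocol 7.2 and 7.3 ask for severity and relatedness on "any adverse event being collected as an endpoint/data point in the study and for all serious adverse events".

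Protocol 10.1 leaves the detailed analyses, and any departure from the protocol, to the SAP. SAP section 1 promises methods for the safety data and mock tables.

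**The concern.** The measure to be analysed is wider than the data that sites must report. A table of treatment-emergent adverse events implies that non-serious events were sought. Here no visible rule asks a site to report a non-serious event as an adverse event. A low non-serious rate could therefore mean few events or few reports. Adjusting for baseline confounders or a propensity score cannot tell these apart, because the uncertainty concerns recording of the outcome and not the patient profile.

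The SAP does not resolve this. A team that follows Protocol 10.2 would produce relative risks on a mislabelled outcome. A team that follows the SAP would find no listed adverse-event output for the SAP's own safety objective. In both cases the secondary safety objective is affected. The primary PGA analysis is not.

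**Working it through.** The documents state no safety figure to reproduce, so the check sets the passages side by side.

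| Question | Analysis text | Collection text |
|---|---|---|
| Which events? | Treatment-emergent adverse events, not limited to serious (Protocol 10.2; SAP 2.10.2) | Spontaneously reported SAEs, plus unusual failure in efficacy and pregnancies (Protocol 7.0); serious events (SAP 2.10.2, recording sentence) |
| Which are coded? | Every adverse event (SAP 2.10.2) | No non-serious event is designated for collection |
| Collection period? | Not given for adverse events in general | Defined for SAEs (Protocol 7.4) |
| Comparison? | Adjusted relative risks over three cohorts (Protocol 10.2) | Not mentioned in the SAP |

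**Step 1. Does any other rule bring in non-serious events?**
- Protocol 7.2 and 7.3 provide for adverse events collected as endpoints or data points, but none of the 13 secondary endpoints (Protocol 5.3.2, i to xiii) is an adverse-event endpoint: 0 of 13.
- Table 1 in both documents covers months 0, 3, 6, 12, 18 and 24. Visits with an adverse-event or SAE row: 0 of 6.
- Endpoint xii comes closest: "Change in medical history and concomitant medication use through the 24 months of treatment will be recorded assessed by the treating physician". Protocol 6.5.1 limits what is kept at follow-up: "only clinically important changes in the Medical History and Physical Examination will be recorded". These are changes in history and examination. No one is asked to identify them as adverse events.
- Protocol 9.0 restricts the CRF to data that the protocol specifies.

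**Step 2. What does the SAP supply?** It has a measure (2.10.2), a MedDRA version (3.1.1) and a Safety population (3.5). Sections 3.6 to 3.12 contain no safety estimator, model, covariate set or definition of treatment-emergent. Of Tables 1 to 60 in the list, adverse-event or SAE tables number 0. The nearest outputs are discontinuation reasons (3.6) and Table 17 (physical and antirheumatic-medication changes).

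**Step 3. What follows for a relative risk?** Take the simplest case of one event per patient and no false reports. Let the true risks be p1 and p2 and the fractions captured c1 and c2. The observed ratio is (c1 × p1) / (c2 × p2) = (p1/p2) × (c1/c2). If c1 = c2 the ratio is unaffected, although each incidence is too low by the factor c. If they differ, the ratio is multiplied by c1/c2. For non-serious events the documents give neither c1 nor c2, and no rule makes either of them high. The incidence cannot be interpreted, and the ratio cannot be verified.

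**The case against.** The best defence has four parts.

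- Protocol 7.0 can be read as a minimum reporting duty and not as a limit on what is collected. Protocol 6.5 asks for all patient-management information, 6.5.1 for all routine laboratory results, and 8.0 for site training in adverse-event reporting. It is true that SAP 2.10.2 does not say that serious events *only* are recorded. But none of these passages designates a non-serious adverse event for collection, so the incidence still has no defined source.
- The SAP is not empty on safety. Its general conventions (3.1.1) call for numbers and percentages under treatment-group headings, so a descriptive incidence could be put together from them. This stands: what is missing is a safety method and a listed output, not every safety element. It also stands that neither document uses the word *all* for the measure. It is simply unrestricted.
- The counts are modest evidence. The SAP places the 13 endpoints under efficacy measures, and spontaneous reporting needs no visit row. The mock tables and the CRF are not in the available text, so 0 of 60 describes the list alone.
- Uniform under-reporting leaves a relative risk intact, as Step 3 shows. This also stands, and it limits what can be claimed about bias.

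**Conclusion.** The mismatch is real and should be corrected. Protocol 7.0, Protocol 10.2 and SAP 2.10.2 cannot all be followed and still yield an adverse-event incidence that means what its label says. SAP 2.10.2 is also inconsistent within itself on what is recorded and what is coded. The SAP does not state whether the relative risks are kept, although Protocol 10.1 says that deviations will be presented there.

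No magnitude of bias is claimed. The conclusion rests on the visible rules and the table list, and it assumes that the CRF adds no undisclosed adverse-event collection.

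Two stronger readings are tempting and are not supported:
- A reader might infer that events are captured more completely in one cohort, so that the relative risks are biased in a known direction. Nothing in the documents shows this: SAP 2.10.2 puts no cohort limit on recording.
- A reader might infer from Protocol 7.5 that SAEs are collected only from users of the sponsor's product. The visible text may describe only a rapid notification route, 7.4 carries no such limit, and part of the section is not available.

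**What to change.** 1. In Protocol 10.2 and SAP 2.10.2, restrict the safety measure to treatment-emergent serious adverse events, in line with Protocol 7.0. Restrict the SAP coding sentence in the same way.
2. Add one table to the SAP: SAEs by cohort, n and %, on the Safety population. State in it how treatment-emergent is defined and to which cohort an event belongs after a treatment switch, since the documents settle neither for safety.
3. In SAP 3.11, record a deviation under Protocol 10.1: adverse-event relative risks will not be produced because non-serious events are not systematically collected, and any SAE comparison is descriptive and limited by spontaneous reporting.
4. Say in the report that non-serious tolerability was not assessed. Narrowing the wording of the safety objectives to match is optional.

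The cost is wording and one table, with no new data. The Protocol 10.2 change would go through the ethics boards. If that is impractical, the SAP entry alone corrects the analysis. The downside is that no adverse-event comparison including non-serious events can be made between cohorts. Keeping one would mean specifying adverse-event collection in all three cohorts, with a matching analysis and tables, and that requires new data collection.

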#### 10.3 Sample Size Calculations

Sample size considerations are based on the primary objectives of the study, specifically the proportion of patients that achieve a PGA rating of "0" or "1" at 24 months of follow up.

The following data and assumptions were used to determine the sample size requirements for the study:

- In the Champion study after 16 weeks of treatment 73% of the patients treated with adalimumab, 30% of the patients treated with methotrexate and 11.3% of the patients treated with placebo achieved PGA values of 0 or 1 indicating clear or minimal disease.
- The Champion study was a randomized placebo controlled clinical trial that was based on a strict protocol not allowing any concomitant treatment and enrolling a very well defined patient population. In the current study we can assume that we will observe similar trends in the order of treatment effectiveness, by which adalimumab will be superior to traditional systemic agents, which will be superior to topical agents. However, due to case mix and use of concomitant medications the actual therapeutic effect and difference between groups may be more variable and lower than that observed in the CHAMPION study. We can therefore assume that due to patient profile, and in order to be conservative, that the observed proportion of patient achieving and maintaining a PGA≤ 1 at 6 months will be approximately 50%. A relative reduction of 20% (RR = 0.80) in PGA would be considered as the minimum acceptable for clinical importance. Therefore, the current study we should be powered to detect a 20% relative reduction between adalimumab and traditional systemic agents, and a similar difference between systemic and topical agents. It follows that if we assume that the proportion of patients treated with adalimumab that achieve PGA ≤1.0 at six months will be

50%, the proportion in the patients treated with traditional systemic agents will be 40% ( $\underline{RR}$ =0.8) and that in patients treated with topical agents will be 32% ( $\underline{RR}$  = 0.8).

• For an expected treatment group ratio of 1:1 for adalimumab: traditional systemic agents and topical agents a total of 360 (180: 180) patients will be required for 80% power and two tailed significance of 5%. Assuming a 25% attrition rate and allowing for 100 additional patients (10 per variable) in the multivariate analysis 660 (330:165:165) patients will be recruited.

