## 2.7 Sample Size

Assuming a 25% attrition rate and allowing for 100 additional patients (10 per variable) in the multivariate analysis, for a treatment group ratio of 2:1:1 for adalimumab, traditional systemic agents and topical agents a total of 660 (330:165:165) patients will be required for 80% power and two tailed 5% significance. In addition, this sample size will be sufficient to detect a 20% (Relative Risk = 0.80) relative reduction in PGA between adalimumab and traditional systemic agents, and a similar difference between systemic and topical agents.

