## 3.10 Analysis of the Primary Objective

For the primary objective, between-group differences with respect to achieving a PGA of "0" or "1" at six months will be assessed with simple logistic regression analysis and multivariate logistic regression models adjusting for potential confounders or the propensity score. In addition, a Generalized Estimating Equation (GEE) model will be used to compare

COMPLETE - PS Statistical Analysis Plan Version 3.0 July 23rd, 2015 Page 30 of 231

the three patient groups in terms of achieving a PGA of "0" or "1" over 24 months of treatment. Kaplan Meier based time to event (survival) analysis will be used with the log-rank test to assess the statistical significance of the between group differences. Cox's proportional hazards model will also be used to adjust for potential confounders or the propensity score.

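### The sample size does not give the stated 80% power for the two contrasts it is meant to power

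*Protocol*

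**What the plan says.** Protocol 10.3 assumes that PGA 0 or 1 at six months is reached by 50% on adalimumab, 40% on traditional systemic agents and 32% on topical agents. Each step is a relative risk of 0.80, which the section treats as the smallest reduction that matters clinically. The study is to be "powered to detect a 20% relative reduction between adalimumab and traditional systemic agents, and a similar difference between systemic and topical agents".

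For a 1:1 ratio the section then gives "a total of 360 (180: 180) patients will be required for 80% power and two tailed significance of 5" percent. It moves to the enrolment target with: "Assuming a 25% attrition rate and allowing for 100 additional patients (10 per variable) in the multivariate analysis 660 (330:165:165) patients will be recruited".

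SAP 2.7 attaches the power to the final number: "a total of 660 (330:165:165) patients will be required for 80% power and two tailed 5% significance". It adds that "this sample size will be sufficient to detect a 20% (Relative Risk = 0.80) relative reduction in PGA between adalimumab and traditional systemic agents", and says the same of systemic vs topical agents.

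The primary objective (Protocol 5.1, SAP 2.3.1) compares adalimumab with topical and with traditional systemic agents. SAP 3.10 plans logistic regression of between-group differences at six months, plus a GEE model to compare "the three patient groups in terms of achieving a PGA of" 0 or 1 over 24 months. It describes no contrast of adalimumab with the two comparators combined.

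**The concern.** A 10-point difference around 45% normally needs close to 400 patients per group for 80% power, and an 8-point difference around 36% needs more than 500. A total of 360 is far below either, and 165 patients in each comparator cohort is too few for both.

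If the power statement is wrong, a non-significant result for adalimumab vs systemic agents could be read as evidence against an important difference when the study had roughly an even chance of missing one. The 360-to-660 step also matters, because a reader should be able to rebuild the enrolment target from the stated allowances.

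**Working it through.** **Inputs.** All are from Protocol 10.3: rates 50%, 40% and 32%; two-sided 5% (z = 1.960); 80% power (z = 0.842); 180:180; 330:165:165; 25% attrition; 100 added patients. One input is assumed: a pooled comparator rate of (40 + 32)/2 = 36%, which needs systemic and topical groups of equal size, as in 165:165.

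**Formula.** Normal approximation for two proportions, no continuity correction. With p̄ the weighted mean rate,

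SE0 = √[p̄(1 − p̄)(1/n1 + 1/n2)], SE1 = √[p1(1 − p1)/n1 + p2(1 − p2)/n2],

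power = Φ[(|p1 − p2| − 1.960·SE0)/SE1].

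**Trying to reproduce 360 (180:180).** The wording of the ratio leaves open which contrast is meant, so each reading was tried.

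- *Adalimumab vs systemic.* p̄ = 0.45, SE0 = 0.05244, SE1 = 0.05217. Power = Φ[(0.10 − 0.10278)/0.05217] = Φ(−0.053) = 47.9%.
- *Adalimumab vs both comparators pooled.* 50% vs 36% is a relative risk of 0.72, not 0.80. p̄ = 0.43, SE0 = 0.05219, SE1 = 0.05166. Power = Φ[(0.14 − 0.10228)/0.05166] = Φ(0.730) = 76.7%.
- *180:90:90 by cohort.* Adalimumab vs systemic 34.0%, systemic vs topical 19.9%, adalimumab vs topical 81.1%.

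Only adalimumab vs topical reaches 80%, and 10.3 does not name it as a sizing target. One-sided testing, continuity correction, unpooled variance and the arcsine method were also tried for the named and pooled contrasts. None came within 3% of 360.

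**Numbers needed for 80% power** (same formula solved for n):

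| Contrast | Ratio | Needed |
|---|---|---|
| 50% vs 40% | 1:1 | 387.3, so 388 per group |
| 50% vs 40% | 2:1 | 582.1 and 291.1, so 583:292 |
| 40% vs 32% | 1:1 | 563.9, so 564 per group |

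**Power at the planned size.** The documents give no time point for the 25% attrition, so both ends are shown. After attrition the groups are 330 × 0.75 = 247.5 and 165 × 0.75 = 123.75.

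| Contrast | No attrition | 25% attrition |
|---|---|---|
| Adalimumab vs systemic, 50% vs 40% | 55.7% | 44.4% |
| Systemic vs topical, 40% vs 32% | 32.7% | 25.7% |
| Adalimumab vs topical, 50% vs 32% | 97.2% | 91.7% |

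For adalimumab vs systemic, the chance of missing the effect is 1 − 0.557 = 44% to 1 − 0.444 = 56%. Unpooled variance moves the figures for the two named contrasts by at most one point.

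**Detectable with 80% power at the planned size:**

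| Contrast | No attrition | 25% attrition |
|---|---|---|
| Adalimumab vs systemic | 50% vs 36.8% (RR 0.74) | 50% vs 34.8% (RR 0.70) |
| Systemic vs topical | 40% vs 25.6% (RR 0.64) | 40% vs 23.5% (RR 0.59) |

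**The step from 360 to 660.** Attrition first, then the added patients: 360/0.75 + 100 = 580. Added patients first: (360 + 100)/0.75 = 613.3, so 614. Neither is 660.

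**The case against.** The best defence is that the authors meant adalimumab vs both comparators together. Two numbers at 1:1, the 330 vs 165 + 165 split, and the recommendation in Protocol 6.2 that half of each site's patients start adalimumab all fit that reading better than a two-cohort comparison that leaves no topical patients in the 360. On that reading 180:180 is only about 3 points short of 80%, and the planned 660 gives 95% (88% after attrition). A three-group chi-square test would have 95% (87% after attrition).

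The number 660 may even have a coherent origin. 50% vs 36% with continuity correction needs 210 per group, 420 in all, and 420/0.75 + 100 = 660.

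These figures are correct, and they show that the study is not underpowered for every question. They do not rescue the text. Neither document claims power for a pooled or three-group comparison; both name the two pairwise contrasts. The stated starting point is 360, not 420, so the origin of 660 is inference.

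It is also fair that these figures describe one unadjusted test at six months. SAP 3.10 adds GEE, log-rank and Cox analyses, and their power was not computed. But the power statement is built on six-month proportions and has to be checked on them.

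**Conclusion.** The power statement is wrong as written in both documents. For the two contrasts they name, 330:165:165 gives 44–56% (adalimumab vs systemic) and 26–33% (systemic vs topical), against a stated 80%. A relative risk of 0.80 is not detectable with 80% power in either, with or without attrition. The 360 is not reproduced for either named contrast or for the pooled one, and 660 does not follow from it.

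The finding is limited to those statements. Adalimumab vs topical, the other half of the primary objective, has 92–97%. Systemic vs topical is outside the primary objective but inside the power claim.

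The figures rest on the protocol's own rates, two-sided 5%, and an unadjusted comparison without allowance for site clustering or multiplicity. At 2.5% per contrast, power at 660 without attrition would be 44% for adalimumab vs systemic and 23% for systemic vs topical.

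**What to change.** 1. In Protocol 10.3, correct or remove the claim that 180:180 gives 80% power. The sponsor should state the contrast, rates, formula and order of allowances actually used for 360 and 660, and the visit to which the 25% attrition applies. If that calculation cannot be recovered, say so, and do not present a reconstruction as the one that was used.
2. In SAP 2.7, delete the claim that 660 is sufficient for a relative risk of 0.80 in each pair, and align the matching sentence in Protocol 10.3.
3. State the power the design has, labelled as unadjusted and as a range with and without attrition: 44–56% for adalimumab vs systemic, 92–97% for adalimumab vs topical, 26–33% for systemic vs topical. Give the detectable differences tabulated above.

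The cost is wording in two documents and a less favourable power statement. No patients are added and no analysis changes.

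### Protocol 10.3: 360 patients give about 77%, not 80%, power if the comparators are mixed equally; 360 does not build up to 660; and the stated power is not tied to a contrast that has it

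*Protocol*

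**What the plan says.** Protocol 10.3 assumes that, on adalimumab, the proportion reaching PGA ≤ 1 "at 6 months will be approximately 50" per cent. The other rates follow by two successive 20% relative reductions: with adalimumab at "50%, the proportion in the patients treated with traditional systemic agents will be 40" per cent, and topical agents at 32%. The section says that the study should be able to detect both steps, adalimumab vs systemic and systemic vs topical.

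The calculation itself uses a 1:1 ratio of adalimumab to systemic plus topical agents and concludes that "a total of 360 (180: 180) patients will be required for 80% power and two tailed significance of 5" per cent. The section then assumes 25% attrition and, "allowing for 100 additional patients (10 per variable) in the multivariate analysis 660 (330:165:165) patients will be recruited".

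SAP 2.7 drops the 360. It restates the design as 2:1:1 and says that "a total of 660 (330:165:165) patients will be required for 80% power and two tailed 5% significance". Its next sentence adds that this number is enough to detect the 20% relative reduction in each of the two pairwise comparisons.

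Neither document gives a combined comparator rate, a formula or the order of the inflation steps. SAP 3.10 analyses PGA 0 or 1 at six months by simple and adjusted logistic regression for between-group differences, without naming a contrast.

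**The concern.** A sample-size paragraph should let a reader go from the assumed rates to the base number and from there to the recruitment target. Here neither step can be reproduced. The base number looks too small for its stated power, and the two stated inflations do not carry it to the total.

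The 1:1 calculation also concerns a pooled comparison, while the surrounding text in both documents claims power for two pairwise comparisons with smaller differences and, at 2:1:1, smaller groups. A reader of SAP 2.7, who no longer sees the 360 or the 1:1 ratio, would take 80% to apply to those pairwise comparisons. What is at stake is how a non-significant pairwise result would be read, more than whether enough patients are recruited.

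**Working it through.** **Inputs.** From Protocol 10.3: two-sided α = 0.05, power 80%, rates 50%, 40% and 32%, base 180:180, attrition 25%, 100 extra patients, total 330:165:165. Inferred, not stated: a combined comparator rate of (40% + 32%)/2 = 36%, from the equal 165:165 split.

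**1. The base figure.** Normal approximation for two proportions, mean rate 0.43, difference 0.14:

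n per group = [1.960·√(2·0.43·0.57) + 0.842·√(0.50·0.50 + 0.36·0.64)]² / 0.14² = (1.3723 + 0.5833)² / 0.0196 = 195.1, so 196 per group and 392 in total.

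Power at 180 per group: z = (0.14·√180 − 1.3723) / 0.6931 = 0.730, which is 76.7%.

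The stated 360 with 80% power is not reproduced by other formulas either:

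| Method | Total for 80% | Power at 180:180 |
|---|---|---|
| Pooled variance | 392 | 76.7% |
| Unpooled variance | 386 | 77.3% |
| Arcsine | 390 | 76.8% |
| Continuity-corrected | 420 | – |
| Exact power of the chi-square test | – | 76.5% |

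A one-sided test would need 154 per group, so it does not explain 180. The named pairwise contrasts fit worse: 180:180 gives 48% for 50% vs 40% and 35% for 40% vs 32%.

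**2. From 360 to 660.** This step needs no assumption about rates.

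- 360/0.75 + 100 = 580
- (360 + 100)/0.75 = 613.3, so 614
- Multiplying by 1.25 instead: 360·1.25 + 100 = 550, and (360 + 100)·1.25 = 575

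The nearest is 660 − 614 = 46 short. Working back from 660:

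- 660·0.75 − 100 = 395, close to the 392 above; (392 + 100)/0.75 = 656
- (660 − 100)·0.75 = 420, the continuity-corrected figure exactly; 420/0.75 + 100 = 660

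**3. What 660 delivers.** 660·0.75 = 495 evaluable, or 247.5 : 123.75 : 123.75. Unadjusted power, pooled-variance formula:

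| Contrast | Rates | Group sizes | Power |
|---|---|---|---|
| Adalimumab vs combined comparators | 50% vs 36% | 247.5 : 247.5 | 88% |
| Adalimumab vs systemic | 50% vs 40% | 247.5 : 123.75 | 44% |
| Systemic vs topical | 40% vs 32% | 123.75 : 123.75 | 26% |

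**4. Adjustment (illustrative).** If covariates explain a share R² of treatment choice, a common approximation takes the effective size as 495(1 − R²). The documents give no R², so a range is shown. Pooled power is 85% at R² = 0.1, 81% at 0.2, 75% at 0.3 and 68% at 0.4. It stays at 80% or more up to 1 − 196/247.5 = 0.21.

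**The case against.** The strongest objection is that 36% is not in the documents, and that the gap at step 1 is small and sensitive. A comparator rate of 35.4%, or adalimumab at 50.6% against 36%, would bring 180:180 to 80%, and the protocol calls its 50% approximate. This stands in part: the 77% is conditional on equal mixing. However, a rate of 35.4% requires a topical share w with 0.40 − 0.08w = 0.354, so w = 0.575, which does not match 165:165. The failure of 360 to reach 660 is unaffected. Adalimumab vs topical at 180:90 would have 81% power, but it is not a 180:180 comparison and is not one of the two named steps.

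A second objection is that the total is sound. It is, for the pooled contrast. A reader might infer from a wrong base figure that 660 is too few; 88% unadjusted power does not support that. Nor can one say which base the sponsor used, because 420 and about 395 both lead to 660.

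A reader might also infer that the sized contrast is never analysed. The documents do not show this. The SAP 3.10 phrase "the three patient groups in terms of achieving a PGA of" belongs to the additional GEE model over 24 months. For the six-month regression no contrast is specified, pooled or pairwise, and the table shells are not in the text available for this review.

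Finally, the ten-per-variable allowance is not claimed to protect power. It is a rule about model size, and in practice the extra patients give headroom. The lack of an adjustment term is therefore a gap in the justification and not an arithmetic error.

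**Conclusion.** The stated base number, its power and the build-up cannot all be right. Given equal mixing of the comparators, 360 gives about 77% power and the base should be 392, or 420 with continuity correction. Independently of that assumption, 360 with the stated inflations gives 580 or 614 and not 660.

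The larger practical consequence is in the wording about contrasts. At 660 with 25% lost, unadjusted power is about 88% for the pooled contrast but about 44% and 26% for the two pairwise contrasts, so the SAP 2.7 statement that 660 suffices for them is not supported by the protocol's own rates. These figures assume that attrition falls equally on the three cohorts and that recruitment follows 330:165:165.

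A reader might go further and conclude that the adjusted analysis is underpowered. That depends on an R² the documents do not give; for the pooled contrast it would be so only above about 0.21. This should be fixed for transparency and correct interpretation. It is not a reason to change recruitment.

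**What to change.** - **Protocol 10.3, base:** correct the 360, state the combined-comparator rate and the formula, and show the build-up actually used: either 420/0.75 + 100 = 660, or (392 + 100)/0.75 = 656 rounded to 660. The sponsor has to say which.
- **Protocol 10.3 and SAP 2.7, power:** attach each power to a named contrast, never a bare figure. With 660 recruited and 25% lost, unadjusted: about 88% for adalimumab vs combined comparators (50% vs 36%), about 44% for adalimumab vs systemic (50% vs 40%), about 26% for systemic vs topical (40% vs 32%). Withdraw the statement that 660 is sufficient for the two pairwise contrasts. Quoting 88% beside that statement without naming the pooled contrast would mislead.
- **SAP 3.10:** name the adalimumab vs combined-comparator contrast at six months, since none is specified now.
- **Optional, labelled as an assumption:** adjusted power for the pooled contrast is about 81%, 75% or 68% if covariates explain 20%, 30% or 40% of treatment choice. Describe the ten-per-variable allowance as a model-size rule.

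The cost is a few sentences in each document and one contrast, with no extra patients. The price is that the documents must state openly that power for the two pairwise comparisons is low.
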